6.4.1. Corticosteroids

To date, corticosteroids use is the only pharmacological intervention that has demonstrated benefit in DMD [[Mendell 1989](#), [Fenichel 1991a](#), [Fenichel 1991b](#), [Griggs 1991](#), [Biggar 2001](#), [Beenakker 2005a](#), [Biggar 2006](#), [Pradhan 2006](#)]. To minimize potential confounding effects of changes in corticosteroid therapy on the interpretation of study results, the use of these medications must be standardized as much as possible during the study.

A stable and standardized corticosteroid regimen should be maintained during the 144 weeks of study drug treatment. Adjustments in corticosteroid dosage for increases in body weight are permitted but are not mandatory. Upward adjustments in corticosteroid dose for increases in body weight or other reasons should follow recommendations provided in Appendix A.

If a patient experiences a concerning corticosteroid-related adverse event (eg. hypertension), interventions or potential adjustments in the corticosteroid dosage may be considered, as detailed in Appendix A. It should be emphasized that reductions in corticosteroid dosage for cosmetic or

other minor reasons should be avoided. Patients who require corticosteroid interruption, dose modification, or reinstatement may remain on study drug therapy.

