10.4.2. Use of Concomitant Medication and Supportive Therapy

Concomitant medications will be coded by means of the World Health Organization Drug Dictionary (WHODRUG) dictionary into Anatomical-Therapeutic-Chemical classification

(ATC) codes. The type and timing of use of specific concomitant medications will be listed and summarized.

Specific attention will be focused on corticosteroid use. The type and duration of pre-study use will be described. The type, dose, schedule, duration of use, dose modifications, dose omissions, and reasons for deviations from initial therapy will be described.

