APPENDIX A. MANAGEMENT OF CORTICOSTEROIDS

A. Initiating Alternate Corticosteroids During the Study

If a patient does require initiation of an alternate corticosteroid therapy (ie. switching from prednisone to deflazacort or vice-versa) during the study, total doses should not exceed 0.75 mg/kg for prednisone and 0.9 mg/kg for deflazacort. General recommendations for corticosteroid dosing are provided in Table A below.

Table A. Guidance for Initiating Alternate Corticosteroid Treatment

Weight Range	Prednisone Dose (0.75 mg/kg)	Deflazacort Dose (0.9 mg/kg)
15-19 kg	12 mg	15 mg
20-25 kg	17 mg	21 mg
26-32 kg	22 mg	27 mg
33-39 kg	27 mg	33 mg
40 kg+	30 mg	36 mg

Patients who require alternate corticosteroid initiation may remain on study drug. Changing the type of corticosteroid or the corticosteroid schedule during the study is strongly discouraged.

B. Maintaining Corticosteroid Dosage During the Study

Adjustments in corticosteroid dosage for increases in body weight are permitted but are not mandatory. If it is the practice of the investigator to adjust patients' corticosteroid doses for changes in body weight, total doses should not exceed 0.75 mg/kg for prednisone and 0.9 mg/kg for deflazacort (see Table A above).

In addition, consistent with the standards proposed for the planned international corticosteroid optimization study [Bushby 2007], increases in total dose for any reasons should not exceed 5 mg for prednisone or 6 mg for deflazacort. For example, if a patient is receiving 22 mg QD of prednisone and it is elected to increase the dose, the total prednisone dose should not be increased beyond 27 mg QD. In addition, for patients ≥ 40 kg, total doses should be capped at 30 mg of prednisone or 36 mg of deflazacort unless the patient was already receiving a higher dose of corticosteroids than these limits at study entry [Bushby 2007].

Patients who require corticosteroid increases may remain on study drug.

C. Modifying Corticosteroid Dosage During the Study

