## 5.5. Concomitant Medications and Procedures

Prior medications and concomitant medications will be coded using the World Health Organization Drug Dictionary (WHODRUG) dictionary dated 2017DEC01 into Anatomical-Therapeutic-Chemical (ATC) classification codes. The prior medications are defined as any medications that subjects started before the first dose date. Concomitant medications are defined as any medications that subjects took after/on the first dose date. The prior and concomitant medications will be summarized by ATC level 3 and preferred terms. The concomitant cardiac medications will be summarized similarly.

Specific attention will be focused on corticosteroid use. The numbers of subjects receiving/not-receiving corticosteroids at baseline or during the study, switching in different types of corticosteroids during the study, and duration of corticosteroid use during the study and by type will be summarized.

The prior and concomitant non-drug therapies will be defined similar to the prior and concomitant medications. They will be coded by MedDRA version 20.1 and summarized by SOC and PT.

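### Table A of Protocol Appendix A gives corticosteroid doses above the appendix's own mg/kg ceiling at the lighter weights of every band below 40 kg

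*Protocol*

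**What the plan says.** Protocol 6.4.1 makes Appendix A the reference for raising a corticosteroid dose: "Upward adjustments in corticosteroid dose for increases in body weight or other reasons should follow recommendations provided in Appendix A".

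Appendix A then sets the same ceiling in two places.

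- **Section A** (changing to another corticosteroid) limits total doses to 0.75 mg/kg for prednisone and 0.9 mg/kg for deflazacort, and continues: "General recommendations for corticosteroid dosing are provided in Table A below".
- **Section B** (adjusting for body weight) repeats the limit and ties it to the table: "total doses should not exceed 0.75 mg/kg for prednisone and 0.9 mg/kg for deflazacort (see Table A above".

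Table A lists a single dose for each weight band. Its column labels carry the same values as the ceiling; the prednisone column, for example, reads "Prednisone Dose (0.75 mg/kg".

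Section B adds two further limits: no increase of more than 5 mg prednisone or 6 mg deflazacort, and a cap of 30 mg or 36 mg from 40 kg upward. The only stated exception is for boys of 40 kg or more who entered the study on a higher dose.

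Two statements narrow who is affected. On switching: "Changing the type of corticosteroid or the corticosteroid schedule during the study is strongly discouraged". On weight-based increases: "Adjustments in corticosteroid dosage for increases in body weight are permitted but are not mandatory".

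**The concern.** A limit that a dose should not exceed has to hold at every weight in a band, so a fixed band dose must be set from the lightest weight in that band. Table A's doses look as if they were set from the middle. A site that reads off the table for a boy near the bottom of a band then gives a dose that the same page says should not be exceeded. Because section B cites the table directly after the ceiling, the site could fairly believe that it is complying.

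This can arise in ordinary use. A growing boy enters each band at its lower limit, where the excess within that band is largest. The increment limit does not prevent it, because the table's steps below 40 kg are exactly 5 mg and 6 mg. Section B's own example, a rise from 22 mg to 27 mg of prednisone, spans two adjacent rows; taken at 33 kg, it satisfies the increment limit and gives 0.82 mg/kg.

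At stake is a clear dosing instruction for children on background therapy, and consistency across sites. Protocol 6.4.1 wants corticosteroid use standardised as far as possible, and here two instructions give different answers at the same weight.

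**Working it through.** **Inputs.** All come from Protocol Appendix A. The ceilings are 0.75 mg/kg (prednisone) and 0.9 mg/kg (deflazacort). The Table A doses are 12, 17, 22, 27 and 30 mg prednisone and 15, 21, 27, 33 and 36 mg deflazacort, for 15–19, 20–25, 26–32, 33–39 and 40+ kg.

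**Step 1. Where the table's doses come from.** Ceiling × band midpoint (17, 22.5, 29, 36 kg):

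- Prednisone: 12.75, 16.9, 21.75, 27.0 mg, against 12, 17, 22, 27 in the table.
- Deflazacort: 15.3, 20.25, 26.1, 32.4 mg, against 15, 21, 27, 33.

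Every row below 40 kg is within 1 mg of the mid-band dose. Read as approximate targets, the figures reproduce. Read as a ceiling for the whole band, they do not.

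**Step 2. Dose per kg at the lower limit of each band.** mg/kg = dose ÷ weight; relative excess = (mg/kg ÷ ceiling) − 1; excess in mg = dose − ceiling × weight.

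| Weight | Prednisone | Excess | Deflazacort | Excess |
|---|---|---|---|---|
| 15 kg | 12/15 = 0.800 | 6.7%; 12 − 11.25 = 0.75 mg | 15/15 = 1.000 | 11.1%; 15 − 13.5 = 1.5 mg |
| 20 kg | 17/20 = 0.850 | 13.3%; 17 − 15 = 2.0 mg | 21/20 = 1.050 | 16.7%; 21 − 18 = 3.0 mg |
| 26 kg | 22/26 = 0.846 | 12.8%; 22 − 19.5 = 2.5 mg | 27/26 = 1.038 | 15.4%; 27 − 23.4 = 3.6 mg |
| 33 kg | 27/33 = 0.818 | 9.1%; 27 − 24.75 = 2.25 mg | 33/33 = 1.000 | 11.1%; 33 − 29.7 = 3.3 mg |
| 40 kg | 30/40 = 0.750 | none | 36/40 = 0.900 | none |

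**Step 3. How far up each band the excess reaches.** Break-even weight = dose ÷ ceiling; any lighter boy in the band is above the ceiling.

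- Prednisone: 12, 17, 22, 27 ÷ 0.75 = 16.0, 22.7, 29.3, 36.0 kg.
- Deflazacort: 15, 21, 27, 33 ÷ 0.9 = 16.7, 23.3, 30.0, 36.7 kg.

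For deflazacort this is past the midpoint of the 20–25, 26–32 and 33–39 kg bands. For prednisone it reaches or just passes the midpoint in the same three bands. In the 15–19 kg band both drugs break even below the midpoint.

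**Step 4. Whole-kg weights above the ceiling, of the 25 from 15 to 39 kg.**

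- Prednisone: 15, 20–22, 26–29, 33–35 = 11, of which 6 by more than 1 mg.
- Deflazacort: 15–16, 20–23, 26–29, 33–36 = 14, of which 10 by more than 1 mg.

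**Step 5. Upper limit of each band (19, 25, 32, 39 kg).** Prednisone 0.632, 0.680, 0.688, 0.692 mg/kg; deflazacort 0.789, 0.840, 0.844, 0.846 mg/kg. All are below the ceiling, so there is no conflict there.

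**The case against.** The strongest reply is that Table A is offered as guidance and general recommendations, so its column labels state a target and the doses are sensible mid-band rounding. The row steps match the increment limits, which suggests a coherent scheme. On this view all that is missing is a word such as approximately. Much of this stands: the doses are reasonable as targets, and the contrast between a limit and a recommendation suggests that the ceiling was meant to govern. It does not remove the conflict. Section B refers to the table immediately after the limit, nothing says which prevails, and rounding to whole milligrams cannot account for 3.6 mg.

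Three stronger readings are tempting, and the documents do not support them.

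- *The excess is a safety hazard.* Nothing presents 0.75 or 0.9 mg/kg as a toxicity threshold. Protocol 6.4.1 gives limiting confounding as the reason for standardising corticosteroids.
- *The SAP has overridden the plan to describe dose.* Protocol 10.4.2 says "The type, dose, schedule, duration of use, dose modifications, dose omissions, and reasons for deviations from initial therapy will be described", whereas SAP 5.5 lists "The numbers of subjects receiving/not-receiving corticosteroids at baseline or during the study, switching in different types of corticosteroids during the study" together with duration and type. SAP 1 does let the SAP prevail where the two conflict, but silence on dose is not shown to be a conflict. SAP 7 does not list it among the changes from the protocol, and SAP 5.1 keeps by-patient listings for every CRF module.
- *About half of the boys are affected.* The 11 and 14 of 25 are counts of weights. The documents give no weight distribution.

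**Conclusion.** The inconsistency is real and follows directly from the printed figures. Following Table A exceeds the stated ceiling at the lighter weights of every band below 40 kg, by 7–13% for prednisone and 11–17% for deflazacort at the lower band limits, and by at most 2.5 mg and 3.6 mg. The excess shrinks to nothing by the break-even weights, and the 40 kg+ row meets the ceiling exactly at 40 kg and is below it above that.

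It is minor. It concerns background therapy, not study drug, and arises only when a boy switches corticosteroid or has an optional weight-based increase. No planned analysis is shown to change. How many boys it touched cannot be told from the documents. The conclusion assumes only that the ceiling applies at the boy's actual weight, which is the plain meaning of a mg/kg limit.

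**What to change.** Add to both section A and section B of Appendix A:

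*Where a Table A dose exceeds 0.75 mg/kg (prednisone) or 0.9 mg/kg (deflazacort) at the patient's actual weight, the mg/kg ceiling applies, rounded down to the nearest available dose.*

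If whole-mg doses are available (an assumption; the documents give no tablet strengths), the limits at 15, 20, 26 and 33 kg become 11, 15, 19 and 24 mg prednisone and 13, 18, 23 and 29 mg deflazacort.

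Table A should not become a binding cap in the upper part of each band, where there is no conflict. At 19 kg that would hold prednisone to 12 mg although the ceiling allows 0.75 × 19 = 14.25 mg, a 16% reduction with no stated reason.

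The cost is one sentence in each of two sections, by clarification letter or with any next amendment. Dosing becomes slightly less convenient than fixed band doses, and rounding down can leave the dose somewhat below the ceiling. For example, if deflazacort came only in 3 mg steps (again an assumption), a 26 kg boy would receive 21 mg, or 0.81 mg/kg, 10% under the limit. SAP 5.2 says that the sponsor has decided to discontinue the study, so the benefit is limited to boys still treated under this appendix.

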APPENDIX B. DECLARATION OF HELSINKI

WORLD MEDICAL ASSOCIATION DECLARATION OF HELSINKI

Ethical Principles for Medical Research Involving Human Subjects

Adopted by the 18th World Medical Association General Assembly Helsinki, Finland, June 1964 and amended by the 29th World Medical Association General Assembly, Tokyo, Japan, October 1975 35th World Medical Association General Assembly, Venice, Italy, October 1983 41st World Medical Association General Assembly, Hong Kong, September 1989 48th World Medical Association General Assembly, Somerset West, Republic of South Africa, October 1996 and the 52nd World Medical Association General Assembly, Edinburgh, Scotland, October 2000

A. Introduction

1. The World Medical Association has developed the Declaration of Helsinki as a statement of ethical principles to provide guidance to physicians and other participants in medical research involving human subjects. Medical research involving human subjects includes research on identifiable human material or identifiable data.
2. It is the duty of the physician to promote and safeguard the health of the people. The physician's knowledge and conscience are dedicated to the fulfillment of this duty.
3. The Declaration of Geneva of the World Medical Association binds the physician with the words, "The health of my patient will be my first consideration," and the International Code of Medical Ethics declares that, "A physician shall act only in the patient's interest when providing medical care which might have the effect of weakening the physical and mental condition of the patient."
4. Medical progress is based on research which ultimately must rest in part on experimentation involving human subjects.
5. In medical research on human subjects, considerations related to the well-being of the human subject should take precedence over the interests of science and society.
6. The primary purpose of medical research involving human subjects is to improve prophylactic, diagnostic and therapeutic procedures and the understanding of the etiology and pathogenesis of disease. Even the best proven prophylactic, diagnostic, and therapeutic methods must continuously be challenged through research for their effectiveness, efficiency, accessibility and quality.
7. In current medical practice and in medical research, most prophylactic, diagnostic and therapeutic procedures involve risks and burdens.
8. Medical research is subject to ethical standards that promote respect for all human beings and protect their health and rights. Some research populations are vulnerable and need special protection. The particular needs of the economically and medically disadvantaged must be recognized. Special attention is also required for those who cannot give or refuse consent for themselves, for those who may be subject to giving consent under duress, for those who will

not benefit personally from the research and for those for whom the research is combined with care.

9. Research investigators should be aware of the ethical, legal and regulatory requirements for research on human subjects in their own countries as well as applicable international requirements. No national ethical, legal or regulatory requirement should be allowed to reduce or eliminate any of the protections for human subjects set forth in this Declaration.

B. Basic Principles for All Medical Research

1. It is the duty of the physician in medical research to protect the life, health, privacy, and dignity of the human subject.
2. Medical research involving human subjects must conform to generally accepted scientific principles, be based on a thorough knowledge of the scientific literature, other relevant sources of information, and on adequate laboratory and, where appropriate, animal experimentation.
3. Appropriate caution must be exercised in the conduct of research which may affect the environment, and the welfare of animals used for research must be respected.
4. The design and performance of each experimental procedure involving human subjects should be clearly formulated in an experimental protocol. This protocol should be submitted for consideration, comment, guidance, and where appropriate, approval to a specially appointed ethical review committee, which must be independent of the investigator, PTC Therapeutics, or any other kind of undue influence. This independent committee should be in conformity with the laws and regulations of the country in which the research experiment is performed. The committee has the right to monitor ongoing trials. The researcher has the obligation to provide monitoring information to the committee, especially any SAEs. The researcher should also submit to the committee, for review, information regarding funding, sponsors, institutional affiliations, other potential conflicts of interest and incentives for subjects.
5. The research protocol should always contain a statement of the ethical considerations involved and should indicate that there is compliance with the principles enunciated in this Declaration.
6. Medical research involving human subjects should be conducted only by scientifically qualified persons and under the supervision of a clinically competent medical person. The responsibility for the human subject must always rest with a medically qualified person and never rest on the subject of the research, even though the subject has given consent.
7. Every medical research project involving human subjects should be preceded by careful assessment of predictable risks and burdens in comparison with foreseeable benefits to the subject or to others. This does not preclude the participation of healthy volunteers in medical research. The design of all studies should be publicly available.
8. Physicians should abstain from engaging in research projects involving human subjects unless they are confident that the risks involved have been adequately assessed and can be satisfactorily managed. Physicians should cease any investigation if the risks are found to

- outweigh the potential benefits or if there is conclusive proof of positive and beneficial results.
9. Medical research involving human subjects should only be conducted if the importance of the objective outweighs the inherent risks and burdens to the subject. This is especially important when the human subjects are healthy volunteers.
 10. Medical research is only justified if there is a reasonable likelihood that the populations in which the research is carried out stand to benefit from the results of the research.
 11. The subjects must be volunteers and informed participants in the research project.
 12. The right of research subjects to safeguard their integrity must always be respected. Every precaution should be taken to respect the privacy of the subject, the confidentiality of the patient's information and to minimize the impact of the study on the subject's physical and mental integrity and on the personality of the subject.
 13. In any research on human beings, each potential subject must be adequately informed of the aims, methods, sources of funding, any possible conflicts of interest, institutional affiliations of the researcher, the anticipated benefits and potential risks of the study and the discomfort it may entail. The subject should be informed of the right to abstain from participation in the study or to withdraw consent to participate at any time without reprisal. After ensuring that the subject has understood the information, the physician should then obtain the subject's freely-given informed consent, preferably in writing. If the consent cannot be obtained in writing, the non-written consent must be formally documented and witnessed.
 14. When obtaining informed consent for the research project the physician should be particularly cautious if the subject is in a dependent relationship with the physician or may consent under duress. In that case the informed consent should be obtained by a well-informed physician who is not engaged in the investigation and who is completely independent of this relationship.
 15. For a research subject who is legally incompetent, physically or mentally incapable of giving consent or is a legally incompetent minor, the investigator must obtain informed consent from the legally authorized representative in accordance with applicable law. These groups should not be included in research unless the research is necessary to promote the health of the population represented and this research cannot instead be performed on legally competent persons.
 16. When a subject deemed legally incompetent, such as a minor child, is able to give assent to decisions about participation in research, the investigator must obtain that assent in addition to the consent of the legally authorized representative.
 17. Research on individuals from whom it is not possible to obtain consent, including proxy or advance consent, should be done only if the physical/mental condition that prevents obtaining informed consent is a necessary characteristic of the research population. The specific reasons for involving research subjects with a condition that renders them unable to give informed consent should be stated in the experimental protocol for consideration and approval of the review committee. The protocol should state that consent to remain in the

research should be obtained as soon as possible from the individual or a legally authorized surrogate.

18. Both authors and publishers have ethical obligations. In publication of the results of research, the investigators are obliged to preserve the accuracy of the results. Negative as well as positive results should be published or otherwise publicly available. Sources of funding, institutional affiliations and any possible conflicts of interest should be declared in the publication. Reports of experimentation not in accordance with the principles laid down in this Declaration should not be accepted for publication.

C. Additional Principles for Medical Research Combined with Medical Care

19. The physician may combine medical research with medical care, only to the extent that the research is justified by its potential prophylactic, diagnostic or therapeutic value. When medical research is combined with medical care, additional standards apply to protect the patients who are research subjects.
20. The benefits, risks, burdens and effectiveness of a new method should be tested against those of the best current prophylactic, diagnostic, and therapeutic methods. This does not exclude the use of placebo, or no treatment, in studies where no proven prophylactic, diagnostic or therapeutic method exists.
21. At the conclusion of the study, every patient entered into the study should be assured of access to the best proven prophylactic, diagnostic and therapeutic methods identified by the study.
22. The physician should fully inform the patient which aspects of the care are related to the research. The refusal of a patient to participate in a study must never interfere with the patient-physician relationship.
23. In the treatment of a patient, where proven prophylactic, diagnostic and therapeutic methods do not exist or have been ineffective, the physician, with informed consent from the patient, must be free to use unproven or new prophylactic, diagnostic and therapeutic measures, if in the physician's judgment it offers hope of saving life, re-establishing health or alleviating suffering. Where possible, these measures should be made the object of research, designed to evaluate their safety and efficacy. In all cases, new information should be recorded and, where appropriate, published. The other relevant guidelines of this Declaration should be followed.
